2.2.4 Peri-Implant Bone Stability

The **fourth** secondary endpoint will be to determine if there are any dimensional changes in bone volume and changes in bone density which will be tracked and qualitatively compared at the following time points: before tooth extraction, at follow-up to the implant placement, six months after functional loading of the implant, and at twelve months after functional loading of the implant. CBCT data will be used to perform these assessments.

2.2.5 Periodontal and Peri-Implant Health

The **fifth secondary endpoint** will be to demonstrate satisfactory periodontal and peri-implant health throughout the 12-month post-functional loading term compared to existing conditions in the oral cavity near adjacent teeth and to baseline around the implant at definitive restoration;

2.2.6 Patient Satisfaction

The **sixth secondary endpoint** will be to demonstrate acceptable level of subject satisfaction after TN-SM device placement and implant uncovering (i.e., level of pain) as well as throughout the 12-month post-functional loading term (i.e., function, level of pain, esthetics). Patient Satisfaction scores will be determined by analysis of patient reports using a Visual Analog Scale.

3 Study Design

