	Crestal bone level maintenance assessed by analysis of two-dimensional periapical radiographic records showing no more than a 2mm loss of height at the 12-month post-functional loading term;
	Dimensional changes in bone volume and changes in bone density will be tracked and qualitatively compared at the following time points: before tooth extraction, at follow-up to the implant placement, six months after functional loading of the implant, and at twelve months after functional loading of the implant. CBCT data will be used to perform these assessments;
	Periodontal and peri-implant tissue health satisfaction demonstrated throughout the 12-month post-functional loading as compared to existing conditions in the oral cavity near adjacent teeth to the implant site and to baseline around the implant at definitive restoration;
	Subject satisfaction after TN-SM device placement and implant uncovering (i.e., level of pain) as well as throughout the 12-month post-functional loading term

	(i.e., function, level of pain, esthetics).						
Primary Analysis:	The primary analysis will be conducted after each subject completes six months of TN-SM device functional loading after crown placement.						
Study Design:	Prospective, multi-center, single arm, clinical pilot study.						
Number of Subjects:	20 subjects total, 10 subjects at each of two Research Centers						
Subject Population:	Male or female subjects 21 years of age or older who require a tooth extraction and desire a replacement with a dental implant and crown reconstruction, and who meet all the Inclusion/Exclusion criteria listed below.						
	The implant site anatomical location may be maxillary or mandibular, anterior or posterior; however, the residual alveolar defect must meet stability and size criteria.						
Inclusion Criteria:	Screening Inclusion Criteria						
	 Subjects must have voluntarily signed the informed consent form before any study related procedures; 						
	• Subjects must be males or females who are a minimum of 21 years of age,						
	 Subjects who require a single tooth extraction and desire a replacement with a dental implant. Candidate subjects may require more than one extraction, but only one site will be considered for inclusion in the study. 						
	 Subjects must have opposing dentition (natural teeth, fixed or removable restorations); 						
	• Subjects must be committed to the study and the required follow-up visits;						
	Subjects must be ASA I or ASA II;						

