	Visit 1	Visit 2	Visit 3	Visit 4	Visit 5	Visit 6	Visit 7	Visit 8	Visit 9	Visit 9.5	Visit 10	Visit 11	Visit 12	Visit 13	Visit 14
Assessments:	Screening Visit ¹	Qualifying Exam	Surgery	Post-Op Follow-up	Implant Uncovering	Restorative Records	Insertion of Definitive Restoration (Baseline)	Follow-up	Follow-up (Primary)	Follow-up	Follow-up	Follow-up	Follow-up	Follow-up	Follow-up
			< 45 days after Screening	2 weeks post- implant placemen t	13 weeks post- implant placement	3 weeks post- implant uncovering	4-6 months post- implant placement	3-months post- loading	6-months post- loading	9-months post- loading	12- months post- loading	15- months post- loading	18- months post- loading	21- months post- loading	24- months post- loading
Pregnancy Test	X ²														
Med & Dental History	х	х	х	х	х	х	х	х	х	х	х	х	х	х	х
Concomitant Medication	х	Х	х	х	х	х	х	х	х	х	х	х	х	х	х
Adverse Event Check			х	х	х	х	х	х	х	х	х	х	х	х	х
Periapical radiographs			Х		х	х	х	х	х		Х		х		х
CBCT – localized		X ³		Х			х	х	х		Х				х
Intra-oral photographs		х	х	х	х	х	х	х	х	х	х	х	х	х	х
Implant stabilization (torque check)			х		х										
Implant success (Buser et al., Error! Bookmark not defined.)								х	х	х	х	х	х	х	х
Oral Hygiene Evaluation	Х	Х	Х	Х	х	х	х	Х	х	Х	Х	х	х	х	х
Periodontal Measurements	Х	Х			х		х	Х	х	Х	Х	х	х	х	х
Peri-Implant Measurements							х	Х	Х	Х	Х	х	Х	Х	х
Subject satisfaction evaluation							х	х	х	х	х	х	х	х	х

¹ The screening assessments can be taken at several visits as long as they are performed within 45 days of the surgery.
 ² The pregnancy test must be administered before taking study required radiographs.
 ³ A localized CBCT is required at screening if a full mouth panoramic radiograph is used at screening instead of the full mouth CBCT.

Table of Contents

CONTACT INFORMATION	2
ABBREVIATIONS	2
SYNOPSIS	4
SCHEDULE OF PROCEDURES / ASSESSMENTS	
TABLE OF CONTENTS	

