3.11.4 Adverse Event Check

Following surgery and at each visit until the end of the study, the Investigator will determine if any adverse events occurred since the last study visit by speaking with the subject and reviewing any dental and medical records. These Adverse Events (AEs), along with any adverse events from the current study visit, should be documented and reported as described in Section 6.3 of the protocol. In addition, the Investigator will evaluate the status of any ongoing adverse events throughout the study as specified in Section 6.4.

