3.11.5 Subject Satisfaction

Subject satisfaction will be assessed utilizing Visual Analog Scales (VAS) at insertion of definitive restoration, as well as at 3-, 6-, 9-, 12-, 15-, 18-, 21-, and 24-months post-functional loading for the following parameters related to the implant and restoration:

• Level of pain associated with the implant and crown

□ Painful □ No pain

- Level of satisfaction with the function of the implant supported crown
 - □ Not satisfied at all □ Highly satisfied
- Level of satisfaction with the esthetics of the implant supported crown

□ Not satisfied at all □ Highly satisfied

Each subject will be asked to complete a VAS for each of the above parameters by the Investigator. The subject will be given a paper questionnaire to mark their responses on the VAS (Appendix 3). The subject will mark a 100 mm scale with a vertical line. A measurement will be made from the left on the scale to the point of the first marking from the subject. This measurement will be recorded on a case report form.

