6.2.4 Severity

Each adverse event should be assessed by the investigator for its severity, or the intensity of an event experienced by a subject, using the following:

- Mild discomfort noticed, but no disruption in daily activities; the event is easily tolerated by the subject
- Moderate discomfort severe enough to reduce or affect normal daily activity
- Severe Inability to work or perform normal daily activity and/or the subject's life is at risk from the adverse event

The maximum severity observed is to be recorded, except if there is a significant worsening in an AE/ADE severity after device intake, then the change will be tracked as a new AE/ADE record as follows:

- The same wording describing the original AE/ADE must be used.
- Outcome of the initial entry should be designated as 'worsened'.
- The end date of the previous AE/ADE must equal the start date of the new AE/ADE.

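### The endpoint calls for a VAS pain score after placement and after uncovering, but no VAS is scheduled until the crown is fitted; two satisfaction lines on the sample form also ask for pain

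*Combined protocol and SAP*

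**What the plan says.** Section 2.2.6 gives the sixth secondary endpoint two time components. The first is an "acceptable level of subject satisfaction after TN-SM device placement and implant uncovering (i.e., level of pain"). The second is pain, function and esthetics over the 12 months after loading. The Synopsis makes the same split: "Subject satisfaction after TN-SM device placement and implant uncovering (i.e., level of pain) as well as throughout the 12-month post-functional loading term". Only one instrument is named: "Patient Satisfaction scores will be determined by analysis of patient reports using a Visual Analog Scale".

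The assessment text starts later. Section 3.11.5 says "Subject satisfaction will be assessed utilizing Visual Analog Scales (VAS) at insertion of definitive restoration" and then every three months to 24 months after loading. Its pain item is "Level of pain associated with the implant and crown". In the assessment schedule, the row "Subject satisfaction evaluation" is marked from Visit 7 onward and is blank before that.

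Before Visit 7, pain could be picked up at the adverse event checks in section 3.11.4, where "the Investigator will determine if any adverse events occurred since the last study visit". Section 6.2.4 adds: "Each adverse event should be assessed by the investigator for its severity". Section 3.11.3 has medication changes recorded at each visit.

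The Appendix 3 sample form has three lines: pain, satisfaction with function, and satisfaction with esthetics. All three carry the same instruction, which asks the subject to mark the pain level. The form is labelled as Visit 9 and as the 12-month visit; in Table 1, Visit 9 is the 6-month visit.

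**The concern.** The endpoint names two early occasions for a patient-marked pain score, and the schedule provides for neither. A site that follows the protocol exactly will reach the analysis with that component empty, and section 7.4.4 rules out imputation.

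The gap is also selective. Sections 3.9 and 5.7 make loading conditional on stability, so a subject whose implant fails before the crown is fitted may never complete a VAS. The satisfaction summary would then describe only subjects who reached loading.

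The form raises a second problem. On the function and esthetics lines, the heading and anchors point to satisfaction while the instruction points to pain. Nothing on a completed form shows which one the subject answered.

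**Working it through.** The documents give no figure to reproduce. The check sets the endpoint against every place that schedules the VAS, then works out the delay and the counts.

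**Where the VAS is scheduled**

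| Source | VAS before Visit 7 | First VAS |
|---|---|---|
| Section 3.11.5 | none | Visit 7 |
| Assessment schedule, satisfaction row | none | Visit 7 (then 8, 9, 9.5, 10, 11, 12, 13, 14) |
| Synopsis visit table | none | Visit 7 |
| Section 3.10 | none | post-loading follow-ups |
| Lists for Visits 3 to 6 (sections 5.3 to 5.6) | none | not applicable |

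Result: 0 VAS occasions at Visits 3 to 6, and 9 from Visit 7 to Visit 14.

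**Delay to the first VAS** (1 month = 30.44 days; visit timing from Table 1)

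- After placement: 4 × 30.44 / 7 = 17.4 weeks to 6 × 30.44 / 7 = 26.1 weeks.
- After uncovering at exactly 13 weeks: 17.4 − 13 = 4.4 to 26.1 − 13 = 13.1 weeks.
- With the ±1 week uncovering window: 17.4 − 14 = 3.4 to 26.1 − 12 = 14.1 weeks.

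**Marks made under the conflicting instruction** (two lines, function and esthetics)

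- VAS visits within the 12-month term are 7, 8, 9, 9.5 and 10, which makes 5.
- All 20 subjects loaded and attending, sample wording at every visit: 5 × 2 × 20 = 200.
- 15 subjects loaded (assumption): 5 × 2 × 15 = 150.
- Wording on one visit's form only: 1 × 2 × 20 = 40.
- Through 24 months, all 9 visits: 9 × 2 × 20 = 360.

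**Could existing visits carry the missing scores?**

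- Visit 4 falls 14 ± 3 = 11 to 17 days after placement (Table 1), or 14 ± 5 = 9 to 19 days (section 5.4).
- Visit 6 falls 21 ± 7 = 14 to 28 days after uncovering (Table 1), or 21 ± 14 = 7 to 35 days (section 5.6). The three to four weeks in section 3.9 (21 to 28 days) lies inside both ranges.
- A question about the first 7 days after each procedure can therefore be answered even at the earliest permitted dates, day 9 and day 7.
- Visit 5 cannot serve for uncovering pain, because the uncovering takes place during that visit.

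**The case against.** The strongest case against concerns weight. This is one component of the last of six secondary endpoints, in a 20-subject single-arm pilot with no hypothesis tests, and no decision rule uses the score. Early pain is not lost to safety reporting: adverse event checks run at Visits 3 to 6, severity is graded, medication changes are recorded, and Table 3 lists pain as an expected effect. All of this stands, and it limits the consequence. It does not supply the endpoint, because a three-level grade recorded by the investigator cannot be summarized as the patient-marked 100 mm score that sections 2.2.6 and 3.11.5 describe.

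One can also argue that Visit 7 is literally after both procedures, so its score could fill the component. That reading is weak. The endpoint sets early pain apart from the loading period, Visit 7 comes 4 to 6 months after surgery, and its item asks about an implant with a crown.

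On the form, the counts are of marks made under an ambiguous instruction, not of wrong marks. The headings and anchors are correct, and the documents show only one sample form. This stands, and it is why the counts are conditional.

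Two further limits stand. Section 2.2.6 sets no threshold for an acceptable level, so extra marks alone would not make that claim demonstrable. Subjects whose implant fails or needs the additional month of healing in section 5.5 may reach Visit 6 late or not at all.

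**Conclusion.** The concern holds. Followed as written, the plan collects 0 VAS pain values before Visit 7 for all 20 subjects, although section 2.2.6 and the Synopsis make early pain a separate, VAS-scored component. The first VAS comes about 17 to 26 weeks after placement and about 3 to 14 weeks after uncovering.

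The form defect is smaller and partly conditional. The wrong instruction on two of the three lines is certain. Its reach within the 12-month term runs from 40 to 200 marks, depending on how many visits use that wording and how many subjects are loaded and attend. The visit label is a clerical error.

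Nothing here touches the primary endpoint or an inferential result. It should still be corrected, because sections 2 and 3.1 make trying out measures for the later study a purpose of this one.

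**What to change.** Choose one of two courses.

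1. **Collect the score.** Add one pain VAS line at Visit 4 for placement and one at Visit 6 for uncovering. Word it for the implant site, without the crown, and state a recall period, for example *worst pain at the implant site in the 7 days after the procedure*. Update section 3.11.5, the assessment schedule, the Synopsis visit table, and sections 5.4 and 5.6. Reconcile the Visit 4 window (±3 days in Table 1, ±5 days in section 5.4) and the Visit 6 window (±1 week in Table 1, ±2 weeks in section 5.6), because they set how far back subjects must recall.
2. **Drop the component.** Delete early pain from the Synopsis and section 2.2.6, and state that it is reported through adverse events.

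In either case, reword the function and esthetics instructions in Appendix 3 to ask for satisfaction, and correct the visit label.

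The first course costs about one minute at each of two visits that subjects already attend, at most 2 × 20 = 40 extra marks, and a revised one-page form. It adds no visits or procedures. Recall at Visit 6 can reach 5 weeks under section 5.6, and longer if healing is extended, so some recall error remains. The second course costs only the text changes and the corrected form.

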3.1 Overview

This is a prospective, multi-center, single arm, pilot clinical study evaluating the use of TN-SM for implant stabilization immediately after tooth extraction. The purpose of this pilot study is to test performance characteristics and capabilities of study design, recruitment criteria, procedures, measures, and operational strategies that are under consideration for use in a subsequent, larger clinical pivotal study. The purpose of the subsequent study will be to provide data demonstrating the safety and efficacy for the use of TN-SM to provide immediate and continued stabilization of implants placed into otherwise unstable sites. Use of TN-SM eliminates the need for the standard practice of bone grafting after tooth extraction and staged implant placement, significantly shortening the overall length of this treatment.

3.2 Intended Use

Tetranite[®] Stabilization Material bonds dental implants to bone in applications where additional mechanical stabilization is required at the time of placement. Its purpose is to augment primary stability of dental endosseous implants inserted into sites that lack adequate primary stability. Tetranite is resorbed over several months while being replaced with new bone without compromising implant stabilization.

3.3 Indications for Use

Tetranite Stabilization Material is indicated to stabilize a dental implant in a compromised implantation site which requires an adjunct to hardware fixation between the implant surface and the bone recipient site. These sites are sockets after the recent extraction of a tooth, that include a surgically created osteotomy within the extraction site made in preparation for dental implant placement in which primary stability is unable to be achieved through conventional means. The adhesive is intended only as an adjunct to hardware fixation and is not intended for stand-alone use.

3.4 Study Population

The study population will consist of male and female subjects at least 21 years of age. The

demographic data will be recorded in the study logs. Subjects will be recruited through the clinics where the investigators are practicing and possibly through referring dentists. There will be a stratified examination of inclusion/exclusion criteria applied during the patient evaluation process to make the process less burdensome to both the potential study subjects and the investigators: the first is the screening criteria of the patient overall, which will consider whole-patient and oral factors, while the second is the extraction site enrollment criteria, which is a more detailed assessment of the candidate study subject and of the specific potential study site which will be determined at the time of the tooth extraction and implant placement. All of the inclusion criteria must be met to receive the study implant. If any of the exclusion criteria are met, the potential study subject must be excluded from the study.

3.5 Study Sample Size

This study size will enroll 20 subjects, 10 at each of the two Research Centers. The enrollment will be capped at 20 subjects total and will not include control subjects.

3.6 Study Duration

The study is expected to enroll 20 subjects over a 6-month period. Study subjects will participate for 30 months (up to 6 months to reach implant loading, then 6 months to reach the primary endpoint, followed by another 18 months to reach 24-months follow-up). The total duration of the study is expected to span 36 months.

3.7 Screening Criteria

Those potential subjects who appear eligible according to the Screening Inclusion and Exclusion Criteria will be asked to provide informed consent in writing prior to any study related procedures and will be considered "consented" in the study and logged in as "consented" candidates. Potential subjects will be evaluated based on the Screening Inclusion Criteria (Section 5.2.2) and Screening Exclusion Criteria (Section 5.2.3) for initial eligibility during the Screening and Examination visits. Subjects must fulfill all of the inclusion criteria and not meet any of the exclusion criteria to be eligible for the study. If the "consented" study candidate meets all the Criteria he/she will be scheduled for the Surgical Visit. If a "consented" study candidate does not meet all the Inclusion/Exclusion Criteria, his/her name will be logged in as a "screen failure". Subject demographics, including age, gender, race, and ethnicity, will be documented at the Examination visit.

3.9 Study Treatment Plan

Subjects enrolled in the study will have had, during the Surgical Visit, a test site which met the criteria of an initially placed implant demonstrating inadequate stability. After implant removal, the TN-SM is applied to the site and the implant is reinserted per the Tetranite IFU – Document # 50001-00 (Appendix 1). Immediate stabilization is assessed by applying a torque of 20 Ncm applied directly to the implant 15 minutes after implantation. This level is a clinically relevant indicator of stability and is expected to be a sub-threshold and nondestructive test.⁴⁸ After successful completion of the torque test, all implants will be closed with a cover screw and soft tissues left to granulate over the socket crests. Monofilament sutures will be used at the discretion of the study site before and after soft tissue adaptation. A standardized periapical image will be captured for documentation of the crestal bone level pre-extraction and after TN-SM device and implant placement.

Two weeks following placement of the TN-SM device and the implant, all subjects will return for evaluation of the study site for healing and possible suture removal. A localized CBCT scan of the region of the study site will be performed and will serve as baseline.

All subjects will return at 13 weeks following the TN-SM device implantation to uncover the implant. At this point, short-term stabilization will be assessed by applying a torque of 35 Ncm to the implant. The test is performed at a clinically relevant torque level to demonstrate readiness for restoration of an implant supported prosthesis.⁴⁹ A healing or standard abutment will be placed during the visit. A standardized periapical image for documentation of crestal bone level and for evaluation of indicators of encapsulation will be captured. Photographic records of the study site will be captured before uncovering surgery and following abutment placement and soft tissue adaptation.

Following a three to four-week healing period, records will be obtained for fabrication of a crown restoration. These records will consist of the following: final impression or scan of the test site dental arch, an impression or scan of the opposing dental arch, a jaw relation record and a shade registration of the dentition. Photographic records will also be captured at this time.

Contingent upon satisfactory stabilization, the implant will be loaded by the implant crown in appropriate occlusion with an abutment and crown prosthesis no sooner than four months and no later than six months after TN-SM device placement. A baseline standardized periapical image for documentation of crestal bone level and for evaluation of indicators of encapsulation will be captured. Photographic records will be captured of the study site before and after the crown is inserted from lingual (or palatal) and from buccal aspects. If the definitive restoration is inserted provisionally at this time, the provisional insertion date will be treated as the baseline loading date for the purposes of the study and the definitive insertion visit will be recorded as a separate visit.

Any loosened implants that are identified during the course of the study will be considered a failure and will be removed. The remaining Tetranite material will be removed by curetting or drilling the osteotomy until a bleeding bone surface is obtained. The clinician may place a wider or longer implant as appropriate for the tooth position. Otherwise the site will be grafted as per a conventional staged approach.

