GBR	Guided Bone Regeneration
GCP	Good Clinical Practice
GTR	Guided Tissue Regeneration
HDD	Horizontal Dimension of Defect
IFU	Instructions for Use
IRB	Institutional Review Board
ISO	International Organization for Standardization
ISQ	Implant Stability Quotient
ITT	Intention To Treat population
mITT	Modified Intention to Treat
mGI	Modified Gingival Index
mm	Millimeter
mSBI	modified Sulcus Bleeding Index

Ncm	Newton Centimeter
PII	Plaque Index
PP	Per Protocol population
PPD	Probing Pocket Depth
PSP	Photostimulable Phosphor
RFA	Resonance Frequency Analysis
SADE	Serious Adverse Device Effect
SAE	Serious Adverse Event
SAF	Safety Population
TN-SM	Tetranite [®] - Stabilization Material
USADE	Unanticipated Serious Adverse Device Effect
VAS	Visual Analog Scale

Synopsis

Oynopsis	
Study Title:	Immediate Placement and Stabilization of Dental Implants with Tetranite [®] Stabilization Material in Mandibular and Maxillary Tooth Extraction Sites that Fail to Provide Adequate Primary Stability – A Pilot Study
Study Protocol Number:	DVAL18041
Study Registration:	This protocol will be registered at www.clinicaltrials.gov before enrollment begins.
Aim:	The aim of this Pilot Study is to demonstrate the safety and efficacy of the use of Tetranite-Stabilization Material (TN-SM) to allow clinical study of the TN-SM device in a greater number of patients.
Primary Endpoint:	 The primary endpoint is a composite measure of implant success (after criteria of Buser, et. al.¹) at six-month post-functional loading consisting of: Presence of the implant at its site of implantation; and,
	Absence of a recurrent peri-implant infection with suppuration; and,
	Absence of mobility, defined as:
	 Lack of implant rotation subjected to 20 Ncm of clockwise torque applied 15 minutes after implant placement; and.
	 Lack of implant rotation subjected to 35 Ncm of clockwise torque applied 13 weeks after implant placement; and,
	 No construct mobility upon palpation at 6 months post- functional loading; and,
	 Absence of encapsulation defined as continuous radiolucency around the implant in a periapical radiograph.
Secondary Endpoints:	Incidence, severity and duration of device-related adverse events throughout the 12-month post-functional loading term;
	Implant success (after criteria of Buser, et. al. ¹ , see primary endpoint) after implants are stabilized with the TN-SM device throughout the 12-month post-functional loading term;

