2.1 Primary Endpoint (Composite)

The **primary endpoint** is implant success through six-months of post-functional loading. The implant success criteria will be collected on a per patient level and are a composite of implant survival, health and efficacy measures, based after criteria of Buser, et. al. ¹, including:

- Presence of the implant at its site of implantation; and,
- Absence of a recurrent peri-implant infection with suppuration; and,
- Absence of mobility, which will be assessed at multiple timepoints. Specifically,
 - Immediate stabilization (implant placement, Visit 3) is assessed by applying a torque of 20 Ncm applied directly to the implant 15 minutes after implantation.
 - Short-term stabilization (implant uncovering, Visit 5) is assessed by applying a torque of 35 Ncm 13 weeks after implant insertion.
 - Continued stabilization is assessed at 6-months post-functional loading (Primary Follow-up, Visit 9) by applying manual palpation.
- Absence of encapsulation determined by a continuous radiolucency around the implant assessed via periapical image.

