3.11 Study Assessments

3.11.1 Implant Success

Implant success will be assessed at post-functional loading follow-ups. A successful implant will meet all of the following criteria according to Buser et al.¹; including,

- Presence of the implant at its site of implantation;
- Absence of a recurrent peri-implant infection with suppuration;
- Absence of mobility, which will be assessed at several timepoints. Specifically,
 - Immediate stabilization (implant placement, Visit 3) is assessed by applying a torque of 20 Ncm applied directly to the implant 15 minutes after implantation.
 - Short-term stabilization (implant uncovering, Visit 5) is assessed by applying a torque of 35 Ncm 13 weeks after implant insertion.
 - Long term stabilization is assessed every 3 months post-functional loading until 24months post-functional loading by manual palpation.
- Absence of encapsulation determined by a continuous radiolucency around the implant recorded in a periapical image.

Any dental implant showing excessive bone loss, radiolucency, or infection shall be treated in the manner best suited to the well-being of the subject, including treatment to save the dental implant. Continuous radiolucency, implant loss, recurrent peri-implant infection with suppuration, or implant mobility shall be considered a failure for the purposes of the study.

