5.5 Implant Uncovering (Visit 5)

At 13 weeks (± 1 week) following implant surgery, the implant will be uncovered, the short-term implant stabilization will be checked, a healing or standard abutment will be placed, and the soft tissue adapted around the abutment. Short-term implant stabilization will be tested by applying a clockwise torque of 35 Ncm to the implant. If the implant does not rotate with torque application, stabilization will be considered a success of the device and the event will be logged as a "success of short-term stabilization". Should the implant rotate with torque application, the abutment will be removed, and the implant will be left and allowed to heal for an additional month and re-evaluated for successful integration. Lack of stabilization will be considered a failure of the device and the event will be logged as a "failure of short-term stabilization". In particular, the subject will have the following procedures and/or evaluations performed and documented at this visit:

- Dental and medical history
- Concomitant medication
- Adverse event check
- Oral hygiene evaluation
- Uncover implant, place healing abutment
- Implant stability by clockwise torque with maximum of 35 Ncm to confirm stabilization
- Standardized periapical radiograph
- Intra-oral photographs

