6.1.2 Serious Adverse Event (SAE)

Any adverse event that:

- led to a death
- led to a serious deterioration in the health of the subject, that either resulted in
 - o a life-threatening illness or injury, or
 - o a permanent impairment of a body structure or a body function, or
- in-patient or prolonged hospitalization, or
- medical or surgical intervention to prevent life-threatening illness or injury or permanent impairment to a body structure or a body function,
- led to fetal distress, fetal death, or a congenital abnormality or birth defect

NOTE: A planned hospitalization for a pre-existing condition, or a procedure required by the protocol, without serious deterioration in health, is not considered to be a serious adverse event.

NOTE: Implant failures requiring the removal of the implant are to be considered a serious adverse event.

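### An implant that rotates at the 13-week torque test is to be removed under 3.9 but left and re-evaluated under 5.5; if it then proves stable, SAE counts differ, and secondary and possibly primary results can differ too

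*Combined protocol and SAP*

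**What the plan says.** **Handling.** Section 3.9 sets a general rule with no time limit and no exception: "Any loosened implants that are identified during the course of the study will be considered a failure and will be removed". Section 5.5, on Visit 5, says that if the implant rotates at 35 Ncm, "the abutment will be removed, and the implant will be left and allowed to heal for an additional month and re-evaluated for successful integration". Neither section refers to the other.

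**Scoring.** Directly after the re-evaluation, 5.5 continues: "Lack of stabilization will be considered a failure of the device and the event will be logged as a" failure of the short-term type. It does not say whether the 13-week test or the re-evaluation decides. The Synopsis makes this a component of the primary composite: "Lack of implant rotation subjected to 35 Ncm of clockwise torque applied 13 weeks after implant placement". It mentions no retest. Section 2.1 says that short-term stabilization "is assessed by applying a torque of 35 Ncm 13 weeks after implant insertion", with no pass/fail rule. Section 3.11.1 repeats the 13-week timing and adds that "implant mobility shall be considered a failure for the purposes of the study".

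**Safety.** Section 6.1.2 notes: "Implant failures requiring the removal of the implant are to be considered a serious adverse event". SAEs go through 24-hour reporting (6.3.2) and adjudication by the Clinical Events Committee (6.4).

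**Secondary success.** Section 2.2.2 lists presence of the implant, infection, mobility by palpation and encapsulation. It contains no torque test.

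**The concern.** Removing an implant and leaving it in place cannot both be done. A center that follows 3.9 and a center that follows 5.5 are each complying with the protocol, yet they treat the same finding differently. The first produces a removal, an SAE, an adjudication and no implant to assess at 12 months. The second may produce none of the first three and an implant that passes every later palpation check.

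The study has 20 subjects at two centers and reports only descriptive results, so the counts are the result. Part of its stated purpose is to test procedures and measures for a larger study. A count that depends on which section a center followed serves that purpose badly.

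**Working it through.** The plan states no power, error rate or derived sample size, so there is no figure of its own to reproduce. The check compares the sections and then sizes the effect on N = 20.

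**1. Does 3.9 reach a rotation at 13 weeks?** Section 3.9 turns on the word *loosened*. Section 5.3.4 uses that word at Visit 3 for an implant that rotated under torque, after its second failed test. Rotation under torque is thus within the protocol's own use of the term, and 3.9 applies throughout the study.

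**2. Can a retained implant go on to the primary visit?** Visit 5 is at 13 ± 1 weeks. One month is 365.25/12/7 = 4.35 weeks, so re-evaluation falls at 12 + 4.35 = 16.3 to 14 + 4.35 = 18.3 weeks. Loading at 4 to 6 months is 17.4 to 26.1 weeks. The implant can therefore still be loaded and assessed at Visit 9. The re-evaluation itself has no scheduled visit, torque level or window.

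**3. Outcomes for one implant that rotates at 13 weeks**

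| | Removed (3.9) | Left, stable at re-evaluation (5.5) | Left, still rotating (5.5) |
|---|---|---|---|
| SAE under the 6.1.2 note | Yes | No | Probably yes, on removal |
| 12-month success as listed in 2.2.2 | Fail | Can pass | Probably fail |
| Primary, Synopsis wording | Fail | Fail | Fail |
| Primary, if the re-evaluation decides | Fail | Pass, if other components are met | Fail |

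Only the middle column diverges. The secondary entry is *can pass* because the Synopsis, unlike 2.2.2, refers the secondary measure back to the primary criteria, which include the torque tests.

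**4. Size.** Each implant in the middle column changes the SAE count by 1. It changes the primary rate by 1/20 = 5 points, but only if the re-evaluation decides. Assume k such implants, all stable at re-evaluation, and no other failures (exact Clopper-Pearson 95% intervals):

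| k | SAEs, removed v. left | Primary, Synopsis wording | Primary, re-evaluation counted |
|---|---|---|---|
| 1 | 1 v. 0 | 19/20 = 95% (75.1–99.9) | 20/20 = 100% (83.2–100) |
| 2 | 2 v. 0 | 18/20 = 90% (68.3–98.8) | 20/20 = 100% (83.2–100) |
| 3 | 3 v. 0 | 17/20 = 85% (62.1–96.8) | 20/20 = 100% (83.2–100) |
| 4 | 4 v. 0 | 16/20 = 80% (56.3–94.3) | 20/20 = 100% (83.2–100) |

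**5. How likely is the handling conflict to arise?** The documents give no 13-week rotation rate, although Table 3 (6.2.6) rates loosening of the implant as probable. With an assumed rate q, the chance of at least one rotation in 20 is 1 − (1 − q)^20: 64% at q = 5%, 88% at 10%, 96% at 15% and 99% at 20%. This is the chance that a center must choose between 3.9 and 5.5. The chance that counts diverge is smaller, because the implant must also recover. For example, q = 10% with half recovering gives 1 − 0.95^20 = 64%.

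**The case against.** A reader might infer that the same 13-week finding necessarily produces different primary results at the two centers, 18/20 against 20/20. The documents do not support that. The Synopsis scores rotation at 13 weeks and allows no retest, and 2.1 and 3.11.1 also place the test at 13 weeks. Section 5.5 attaches its short-term success label only to no rotation at that test. Section 5.3.4 expressly logs a second-attempt pass at Visit 3 as a success; 5.5 has no such sentence for its re-evaluation. Its failure sentence can be read as the counterpart of the 13-week success sentence, with the extra month being care of the implant. This objection largely stands. What remains is that the sentence order in 5.5 leaves the deciding test open, and that a center could reason by analogy with Visit 3.

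It can also be said that 3.9 is the general rule for a confirmed loose implant and 5.5 the specific rule for Visit 5. In support, 5.3.4 uses *loosened* only after a second failed test. That is a plausible reading, but no text states it, and 3.9 is worded without exception.

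Finally, this is a single-arm pilot with no hypothesis test and no success threshold, so no formal decision changes. That is correct and limits the consequence. It does not remove the conflict in handling or its effect on the SAE count.

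**Conclusion.** The conflict between 3.9 and 5.5 is real and wrong as written. For an implant that rotates at 13 weeks and is stable at re-evaluation, it changes the SAE count by one, and on the 2.2.2 wording it can change the 12-month success result. Neither effect depends on how the primary composite is read.

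The primary effect is conditional: up to 5 points per such subject, and only where a center treats the re-evaluation as the deciding test. If the implant still rotates at re-evaluation, both routes probably end in failure, removal and an SAE, and nothing diverges. The numbers of rotating and recovering implants are assumptions throughout, because the documents give neither.

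**What to change.** 1. Reconcile 3.9 and 5.5 on how an implant that rotates at the 13-week test is handled, and cross-refer the two sections. This review takes no view on which handling is right. A single rule removes the divergence in SAE counts and in secondary success.
2. State in 2.1, 3.11.1 and 5.5 that the 13-week torque result is the component that enters the primary composite, as the Synopsis already says. State in 5.5 that this test produces the logged short-term success or failure.
3. Report any re-evaluation separately, as a descriptive outcome.

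The cost is protocol wording, with no added subjects or visits. The downside is that the primary rate may be less favourable than if recovered implants were counted as successes.
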